### 5.6.2.2 Overall Response Rate (ORR)

Overall response rate (ORR), i.e. rate of patients with response (CR+PR for RECIST V1.1), will be presented together with corresponding Clopper-Pearson 95% CI for each dose group with at least 6 patients. For changes in solid tumour size, waterfall plots will be presented. For all response assessments, swimmers plots will be presented. All response assessments will be listed.

For T-ALL/T-LBL patients, the overall bone marrow response rate as per local assessment, the number (n) and percentage (%) of patients with progressive disease [PD], refractory and relapsed disease will be summarized by cycle and overall for each dose group and overall, with 95 % CI. In addition to bone marrow the mediastinal response, CNS and extramedullary responses will be presented in the same way but only for subset of patients with extramedullary involvement at baseline. Swimmers plots will be generated for graphical display of response. Clopper-Pearson (exact) method will be used to derive the CI.

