## **EFFICACY ANALYSES**

Overall response rate as defined by achieving:

- In solid tumours, confirmed complete response (CR) and/or partial response (PR) will be presented by percentage rates and 95% confidence intervals (CI). For changes in solid tumour size, waterfall plots will be presented.
- In T-ALL/T-LBL patients, confirmed Complete Remission (CR) and/or Complete Remission with Incomplete Hematologic Recovery (CRI) will be presented by percentage rates and 95% CI.
- For solid tumour indications: clinical benefit rate at Month 3, 6, and 9, as defined by achieving complete response (CR) and/or partial response (PR) and/or stable disease (SD) will be assessed by RECIST 1.1 and presented by percentage rates and 95% CI. Waterfall plots will be presented.
- For T-ALL/T-LBL patients: the ORR is the sum of patients achieving a CR or a CRI divided by the total number of patients with T-ALL/T-LBL treated. Assessment of efficacy will be performed on results of bone marrow biopsies or aspirates, blood and CSF samples, and PET-CT in patients with extramedullary disease, based on the NCCN Guidelines on Adult Acute Lymphoblastic Leukemia (Version 1.2020).

For all response assessments, swimmers plots will be presented. All response assessments will be listed.

The duration of response defined as time from first assessment of PR or CR in solid tumours or CRI in T-ALL/T-LBL to follow-on first assessment of PD or relapse will be summarised by descriptive statistics including median duration of response and respective 95% CI. Duration of response will also be listed.

Time from first treatment received until progressive disease (PD)/OS will be summarised by Kaplan-Meier estimates, median PFS/OS and respective 95% confidence intervals. Patients with no event will be censored at the last available tumour assessment for PFS and at the last timepoint known alive for OS.

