#### 1. Disease

- a. Histologically or cytologically confirmed solid tumours that are surgically unresectable, locally advanced, or metastatic, which have progressed on at least one line of systemic therapy (with the exception of ACC patients who are allowed to be systemic treatment-naïve) and for which no established therapeutic alternatives exist.

or

- b. Relapsed or refractory (r/r) T-ALL or T-LBL. Refractory patients are defined as T-ALL/T-LBL patients with  $\geq 5\%$  bone marrow blasts and/or concomitant extramedullary involvement, who have not achieved a CR after standard induction/consolidation therapy attempt. Relapsed patients are defined as T-ALL/T-LBL patients who have recurrent disease, i.e.  $\geq 5\%$  bone marrow blasts and/or concomitant extramedullary relapse, after having achieved a prior CR.
- c. For **Part A (dose-escalation)** solid tumour indications based on known frequent involvement of the NOTCH pathway activation in these indications, and tumours with an *a priori* known NOTCH1-4 pathway activation are also eligible, as defined below:
  - Breast cancer (TNBC, ER+/-, HER2+/-), GI cancers (resistant to oxaliplatin or irinotecan-based therapy colorectal cancer, hepatocellular carcinoma), osteosarcoma, ACC and malignant glomus tumour.
  - Any other solid cancer (including lymphoma) with a confirmed NOTCH1-4 activating mutation or genetic lesion.
- d. For **Part A (MTD/RP2D confirmatory cohort) and Part B expansion cohorts**, solid and haematological tumour indications with confirmed Notch pathway activation as follows:
  - ACC
  - Metastatic breast cancer (regardless of receptor status of ER/PR, HER2)
  - r/r T-ALL/T-LBL
  - Any other cancer (haematologic or solid) with a confirmed NOTCH pathway activation, after approval by the Sponsor

---

CONFIDENTIAL

May not be used, divulged, published, or otherwise disclosed without the consent of Cellestia Biotech AG

Notes:

- Patients are eligible if Notch pathway activation was determined in the past. If the Notch status is unknown, it will be determined on fresh bodily material.
  - The pathogenic character of the detected mutation/genetic alteration needs to be confirmed before the patient can be enrolled. Patients whose tumour mutations/alterations are not unambiguously pathogenic will be included at the Sponsor's discretion. Details on molecular alterations as signs of Notch pathway activation and the specific test method can be found in the laboratory manual.

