## **Appendix 8 Response Assessment in Acute Lymphoblastic Leukaemia/ Lymphoblastic Lymphoma**

### **Response criteria for Blood and Bone Marrow:**

- CR
  - No circulating lymphoblasts or extramedullary disease
  - No lymphadenopathy, splenomegaly, skin/gum infiltration/testicular mass/CNS involvement
  - Trilineage haematopoiesis (TLH) and <5% blasts
  - Absolute neutrophil count (ANC) >1000/microL
  - Platelets >100,000/microL
  - No recurrence for 4 weeks
- CR with incomplete blood count recovery (CRi)
  - Meets all criteria for CR except platelet count or ANC
- Overall response rate (ORR = CR + CRi)
- **NOTE:** MRD assessment is not included in morphologic assessment and should be obtained
- Refractory disease
  - Failure to achieve CR at the end of induction
- Progressive disease (PD)
  - Increase of at least 25% in the absolute number of circulating or bone marrow blasts or development of extramedullary disease
- Relapsed disease
  - Reappearance of blasts in the blood or bone marrow (>5%) or in any extramedullary site after a CR

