## **6. Changes in the Conduct of the Study or Planned Analysis**

There were no changes in the analysis planned in the protocol of the study at the time of preparing this SAP.

Any deviations from the approved SAP will be described and justified in the CSR.

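### SAP 5.6.2.2 puts an undefined bone marrow response rate where the protocol's T-ALL/T-LBL overall response rate should be

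*SAP*

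**What the plan says.** **Protocol.** The Synopsis (Efficacy Analyses) gives numerator and denominator: "the ORR is the sum of patients achieving a CR or a CRI divided by the total number of patients with T-ALL/T-LBL treated". It bases the assessment on marrow samples together with "blood and CSF samples, and PET-CT in patients with extramedullary disease". Section 10.6.2 adds that the CR or CRi must be confirmed and that the rate carries a 95% CI. In Appendix 8, the criteria list for blood and bone marrow opens CR with "No circulating lymphoblasts or extramedullary disease". CRi relaxes only the platelet and neutrophil conditions, and newly developed extramedullary disease is progression.

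**Eligibility.** Inclusion criterion 1b defines refractory disease by at least 5% "bone marrow blasts and/or concomitant extramedullary involvement, who have not achieved a CR". The relapsed definition has the same and/or structure.

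**SAP.** The leukaemia paragraph of 5.6.2.2 begins "For T-ALL/T-LBL patients, the overall bone marrow response rate as per local assessment". It adds counts of progressive, refractory and relapsed disease, by cycle and overall, with 95% CIs. Mediastinal, CNS and extramedullary responses are then presented in addition to marrow, but "only for subset of patients with extramedullary involvement at baseline". Elsewhere, 2.6 keeps CR or CRi per NCCN as the secondary endpoint. Section 5.6.2.1 uses it as the responder rule for best overall response (BOR), with confirmation after at least 4 weeks, and tabulates BOR by cohort for haematologic malignancies. Section 5.6.2 lists overall NCCN response by cycle. On departures from the protocol, section 6 states: "There were no changes in the analysis planned in the protocol".

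**The concern.** The section of the SAP that should turn the protocol's ORR into a calculation names a different quantity for this disease. The marrow rate has no definition, no reference to Appendix 8, no confirmation requirement in its own paragraph and no rule for combining sites. The other sites are limited to patients involved there at baseline. The marrow rate has no matching limit to patients with marrow disease at baseline.

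Two things are at stake. First, a programmer working from 5.6.2.2 could produce a T-ALL/T-LBL response rate that differs from the CR/CRi count in the BOR table, and nothing says which of the two is the endpoint. Second, on a site-by-site reading, some patients could meet a marrow blast threshold at entry and be counted as responders while their disease, which lies outside the marrow, has not responded.

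**Working it through.** The documents state no T-ALL/T-LBL sample size, assumed rate or power for Part A, so there is no figure to reproduce. The check compares definitions and then shows how far the rate could move.

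**Step 1. The definitions side by side**

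| Element | Protocol (Synopsis; 10.6.2; Appendix 8) | SAP 5.6.2.2, T-ALL/T-LBL paragraph |
|---|---|---|
| Response | CR or CRi | Marrow response, undefined |
| Sites | Marrow, blood, CSF, PET-CT if extramedullary disease | Marrow; other sites reported separately |
| Confirmation | Required | Not mentioned here (required in 5.6.2.1) |
| Denominator | All treated T-ALL/T-LBL patients | Not stated; no baseline marrow condition |
| 95% CI | On the CR plus CRi rate | On the marrow rate |

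**Step 2. Two ways to score marrow response**

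- *Full Appendix 8 list for blood and marrow.* Extramedullary disease bars CR and therefore CRi, and new extramedullary disease is progression. The number of extra responders is k = 0.
- *Marrow as one site among several.* The SAP's contrast between marrow and the mediastinal, CNS and extramedullary responses suggests this reading. A patient admitted through the and/or wording of criterion 1b with under 5% marrow blasts could then be counted, so k could be 1 or more.

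**Step 3. Size if k is not zero**

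With x composite responders among n patients, the reported rate is (x + k)/n. The inflation is 100k/n points, or 100/n per patient: 100/6 = 16.7, 100/10 = 10.0 and 100/20 = 5.0.

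The intervals use Clopper-Pearson, the SAP's own method. For y = x + k responders, the lower limit is the 2.5% quantile of Beta(y, n − y + 1) and the upper limit is the 97.5% quantile of Beta(y + 1, n − y). All n, x and k are assumptions.

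| n | x | k | Rate | 95% CI |
|---|---|---|---|---|
| 6 | 1 | 0 | 16.7% | 0.4 to 64.1 |
| 6 | 1 | 1 | 33.3% | 4.3 to 77.7 |
| 10 | 2 | 0 | 20.0% | 2.5 to 55.6 |
| 10 | 2 | 1 | 30.0% | 6.7 to 65.2 |
| 10 | 2 | 2 | 40.0% | 12.2 to 73.8 |
| 20 | 3 | 0 | 15.0% | 3.2 to 37.9 |
| 20 | 3 | 2 | 25.0% | 8.7 to 49.1 |

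**Step 4. Can the protocol rate be recovered from the BOR table?**

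Only in part. The count of CR plus CRi should be there, because 5.6.2.1 names both as response. But its ordering for picking the best response runs CR, PR, SD, PD, NE/UNK and has no place for CRi. The section also assigns no interval to the CR plus CRi rate.

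**The case against.** The strongest reply is that the SAP already contains the right endpoint. CR or CRi per NCCN is the secondary endpoint in 2.6 and the confirmed responder rule in 5.6.2.1, and 5.6.2.3 uses confirmed NCCN response for duration of response. The opening sentence of 5.6.2.2 describes ORR as the rate of patients with response, with a Clopper-Pearson interval, and does not expressly exclude leukaemia. The outcomes in the T-ALL/T-LBL paragraph (progressive, refractory, relapsed) mirror Appendix 8's blood and marrow list. The separately reported sites broadly match the lists that follow it. Read that way, marrow response means the full list and nobody with extramedullary disease can be CR or CRi.

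Much of this stands. A reader might infer that the SAP has replaced the composite endpoint; it has not. A reader might also infer that patients with active or new extramedullary disease will be counted as responders. The documents do not prescribe that. It follows only from a blast-count reading of an undefined term, and new extramedullary disease is progression, which 5.6.2.2 tabulates without restricting it to the baseline-involved subset.

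The reply does not close the gap. The only bracketed definition in the opening sentence of 5.6.2.2 is CR plus PR by RECIST, which does not fit leukaemia. The paragraph written for leukaemia then names something else and sets marrow against the other sites. The Appendix 8 reading is reasonable, but the SAP does not state it.

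On section 6, the SAP cites protocol version 4.1 and the version available is 4.3. Whether the statement of no changes was accurate when written therefore cannot be fully tested.

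**Conclusion.** The point holds as a specification defect of moderate severity. For T-ALL/T-LBL, SAP 5.6.2.2 gives the interval to an undefined marrow rate and does not expressly specify the protocol's ORR. The possible inflation is 100/n points for each patient whose marrow alone is scored as response, and zero under the full Appendix 8 criteria. The documents do not settle which scoring applies, so upward bias is a possibility and not a finding. The non-zero case also assumes that criterion 1b admits patients with under 5% marrow blasts. Its and/or wording allows this, although the word concomitant leaves some doubt.

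The consequences are limited. Response rate is secondary in Part A, whose primary endpoints are DLTs and safety. No hypothesis test is planned and no Part A decision uses this rate.

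A reader might carry the problem into Part B, where this arm succeeds if the model's point estimate exceeds 40%. The documents do not support that step. This SAP covers Part A only, and protocol 4.2.1 sets the Part B endpoint as confirmed CR and CRi. Qualifying confirmatory-cohort patients do enter the Part B analysis, but nothing says the Part A marrow definition goes with them. Nor does a simple projection show the bar being passed. With an assumed 20% composite rate and 25% of patients wrongly counted, the result is 0.25 + 0.75 × 0.20 = 0.40. That equals 40% without exceeding it, both inputs are assumed, and it is a raw proportion rather than the hierarchical model's estimate.

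**What to change.** In SAP 5.6.2.2, define the T-ALL/T-LBL ORR as patients with confirmed CR or CRi per Appendix 8, all sites considered, divided by all treated T-ALL/T-LBL patients, with a Clopper-Pearson 95% CI. In 5.6.2.1, give CRi a place in the BOR ordering. Keep marrow response as a supportive table: state its criteria and restrict it to patients with at least 5% marrow blasts at baseline.

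The cost is some SAP wording and one derived variable from assessments already collected. The reported rate may turn out lower than the marrow rate would have been.

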### 5.6.2.3 Time to response (TTR) and Duration of response (DOR)

TTR is defined as the time from the first day of study treatment to the first date the response criteria are met, given they were later confirmed. Patients who are not confirmed responders will be censored at the time of their last evaluable tumour assessment. Patients with no tumour assessment after the baseline visit will be censored at the time of the first day of study treatment plus 1 day.

For each dose group, estimates of the median TTR and the corresponding two-sided 95% CI will be presented along with the estimates for the 25th and 75th percentiles and the associated ranges (minimum, maximum) using the Kaplan-Meier (KM) approach.

DOR is defined only for the patients with a confirmed response according to RECIST, v1.1 for patients with solid tumours, according to NCCN guidelines for patients with haematologic malignancies.

By definition, DOR is the time interval between the date of the earliest qualifying response and the date of PD or death from any cause, whichever occurs first. For patients who are alive without progression following the qualifying response, DOR will be censored on the date of last evaluable tumour assessment or last FU for PD before the data cutoff date. Data for patients who are lost to FU prior to documented progression will be censored at the last tumour assessment date which the patient is known to be progression-free prior to the data cutoff date.

For each cohort, estimates of the median DOR and the corresponding two-sided 95% CI will be presented along with the estimates for the 25th and 75th percentiles and the associated ranges (minimum, maximum) using the Kaplan-Meier (KM) approach.

Both TTR and DOR will be provided in Listing.

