**9.2.4 Criteria for Withdrawal from the Study**

Patients will be withdrawn from the study if the following criteria are met:

- Unequivocal disease progression
- Death
- Intervening illness that prevents further administration of treatment
- Unacceptable adverse events
- Intercurrent cardiac disease, especially drop in LVEF < 40% or drop > 15% from baseline (if LVEF with > 15% drop is still > 55% a second measurement after 1 week would be allowed before discontinuing the patient)
- Intercurrent interstitial lung disease or pneumonitis
- Patient non-compliance
- Pregnancy
- The patient decides to withdraw from study or is lost to follow-up
- General or specific changes in the patient's condition that render the patient not eligible for further treatment in the judgment of the Investigator
- If a patient experiences a DLT
- If a patient requires a continuous dose delay of more than 14 days (Part A and Part B) from the intended day of the next scheduled dose of CB-103
- If a patient is non-compliant and misses or forgets more than 3 sequential dosings on more than 1 occasion

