### 5.6.2.1 Best Overall Response (BOR)

BOR is defined as the best response recorded from the first day of study treatment until disease progression/recurrence, death or end of study respectively data cut-off, whatever comes first.

Patients with solid tumours are considered responders if they have a tumour assessment status of PR or CR according to RECIST, v1.1.

The best overall response is the best response recorded from the start of the treatment until disease progression/recurrence. Best is defined as the first response when all a subject's response assessments are sorted by CR, PR, SD, PD, NE/UNK. In general, the subject's best response assignment will depend on the achievement of the measurement criteria. For subjects without a post-baseline, a non-missing response assessment will have a BOR of NE assigned. Unknown (UNK) or patients with symptomatic deterioration but without any scan will also be mapped to NE.

Patients with haematologic malignancies are considered responders if they have a haematologic malignancies status CR or CRi as per NCCN guidelines.

Any response must be confirmed not less than 4 weeks after the criteria for response are first met.

Patients without a post-baseline assessment will be considered NE. Additionally, after baseline, a change in methods will result in an assessment of not evaluable.

Patients who were enrolled in study, but did not receive any study treatment will have a best overall response 'Missing' and will be included as non-responders in the analysis of BOR.

BOR for different cancer types will be summarized by cohort for patients with Solid Tumour and for those with haematologic malignancies. The BOR information will be provided in Listing.

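### Kaplan-Meier time to response censors progressors and deaths, so its median and quartiles describe neither the responders nor the whole dose group

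*SAP*

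**What the plan says.** TTR is a secondary endpoint (Protocol 4.2.2, SAP 2.6). Protocol 10.6.2 gives no method for it, so SAP 5.6.2.3 is the only specification.

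- Event: "TTR is defined as the time from the first day of study treatment to the first date the response criteria are met", provided the response is later confirmed.
- Censoring: "Patients who are not confirmed responders will be censored at the time of their last evaluable tumour assessment". Also: "Patients with no tumour assessment after the baseline visit will be censored at the time of the first day of study treatment plus 1 day". There is no separate rule for progression or death.
- Output: "For each dose group, estimates of the median TTR and the corresponding two-sided 95% CI will be presented", with quartiles and range, by Kaplan-Meier, plus a listing.

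The response window is set in SAP 5.6.2.1: "BOR is defined as the best response recorded from the first day of study treatment until disease progression/recurrence, death or end of study". Protocol 9.2.4 lists "Unequivocal disease progression" among the criteria for withdrawal from the study. For duration of response (DOR), the same SAP section restricts the analysis to confirmed responders.

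**The concern.** Under the SAP's own definition, a patient who has progressed or died can no longer become a responder. Kaplan-Meier treats a censored patient as someone whose later course would resemble that of patients still under observation. Applied here, it assumes that progressors would have gone on to respond at the same rate as those who did not progress. That makes the censoring informative.

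The planned percentiles are read off this curve. A median TTR can then be printed although far fewer than half of the patients respond, and it will not match the timing seen in those who did. A reader would naturally take it for one or the other.

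**Working it through.** The documents give no TTR figure, so there is nothing to reproduce. The check compares the SAP rule with two alternatives on assumed data.

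**Scan times.** SAP Appendix 3 (notes 21 and 22) gives week 6, then every 8 weeks, then every 12 weeks after cycle 6. This is taken as weeks 6, 14, 22, 34, 46 and 58.

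**Assumed data.** There are 20 patients. Six are confirmed responders (weeks 6, 6, 14, 14, 22, 34). Twelve progress, last assessed at week 6 (6 patients), week 14 (3), week 22 (2) and week 34 (1). Two are still followed beyond week 34.

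**SAP rule.** S(t) is the product of (1 − responses / number at risk).

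| Week | At risk | Responses | Factor | S | Progressors then censored |
|---|---|---|---|---|---|
| 6 | 20 | 2 | 18/20 | 0.900 | 6 |
| 14 | 12 | 2 | 10/12 | 0.750 | 3 |
| 22 | 7 | 1 | 6/7 | 0.643 | 2 |
| 34 | 4 | 1 | 3/4 | 0.482 | 1 |

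One minus Kaplan-Meier is 1 − 0.482 = 51.8%. S first falls below 0.5 at week 34, so the median TTR is 34 weeks.

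**Competing-risk version.** Cumulative incidence sums (share still free of response and progression) × (responses / number at risk): 2/20 + (12/20)(2/12) + (7/20)(1/7) + (4/20)(1/4) = 0.10 + 0.10 + 0.05 + 0.05 = 30%. This equals the ORR of 6/20. The median is not reached.

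**Responders only.** The median of 6, 6, 14, 14, 22, 34 is 14 weeks (range 6–34).

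**How far this generalises.** The simulation used 1,500 replicates per setting, ORR of 5% to 30% and exponential progression in non-responders with median 13 or 26 weeks. Responses fell at weeks 6–22 or weeks 6–34. All of these are assumptions; the documents state no response rate for Part A. Results for a group of 45, the approximate size of the confirmatory cohort (SAP 2.3):

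| Progression median; responses | Mean 1−KM / ORR, over ORR 5–30% | ORR 20%: first quartile reached (observed ORR ≥25%) | ORR 30%: median reached (observed ORR ≥50%) |
|---|---|---|---|
| 26 wk; to wk 22 | 1.12–1.14 | 33.9% (16.1%) | 1.9% (0.1%) |
| 26 wk; to wk 34 | 1.23–1.29 | 50.3% (18.6%) | 5.7% (0.2%) |
| 13 wk; to wk 22 | 1.26–1.33 | 51.7% (17.1%) | 9.1% (0.3%) |
| 13 wk; to wk 34 | 1.54–1.73 | 74.8% (18.1%) | 35.5% (0.3%) |

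Over groups of 6, 20 and 45 the mean ratio ran from 1.11 to 1.75.

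**Which progression rate is nearer?** Protocol 2.5.6 reports 68% disease control at 3 months in 19 patients with adenoid cystic carcinoma (13/19). Treat loss of control as progression, 3 months as 13 weeks and the hazard as constant. The median is then 13 × ln 2 / −ln(13/19) = 9.01 / 0.379 ≈ 24 weeks, closer to the milder rows. It covers that tumour type only.

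**Small groups.** Take 6 patients and one confirmed responder (ORR 16.7%). One minus Kaplan-Meier is 1/6 = 16.7% if the response is at week 6. It is 1/4 = 25% at week 14 after two progressions at week 6. It is 100%, with a median TTR of 22 weeks, if the responder is the only patient still at risk at week 22.

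**The case against.** Much of the opposing case stands.

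- A reader might infer that the SAP reports response probabilities above the ORR. It does not. SAP 5.6.2.3 plans percentiles, a range and a listing, with no response probability and no TTR curve. The response rate comes from SAP 5.6.2.2, with an exact confidence interval, and this rule does not touch it. The distortion reaches the report only through the quartiles and the median.
- A reader might infer that the error always flatters the drug. That depends on the comparator. Against a competing-risk median that is not reached, a finite Kaplan-Meier median flatters. Against the responders' median it looks slower: 34 weeks versus 14 in the example.
- It would be wrong to say that progressors are kept at risk. Censoring removes them. The fault is the assumption that their removal says nothing about future response.
- More extreme examples can be built, but they must respect SAP 5.6.2.1, which requires confirmation at least 4 weeks later. A patient whose last scan is the first to show response is not an event.
- SAP 5.1 limits Kaplan-Meier output to groups with enough patients, and the listings and swimmers plots show individual timing. However, the SAP 5.1 threshold is undefined, and TTR lacks the at-least-6 limit given for ORR, clinical benefit rate, PFS and OS.
- Best response was stable disease at the August 2020 cut-off (Protocol 2.5.6). With no responders there is nothing to estimate or distort.

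Censoring is reasonable for patients still on study without progression. It is not reasonable for progression and death, and none of the points above changes that.

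**Conclusion.** The point holds as a flaw in how a secondary endpoint is summarised. Followed exactly, the rule can print a median or quartile that is neither the responders' timing nor the time by which that share of the group responded.

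The size is conditional: nil when all responses occur at the first scan or nobody responds, and about 1.1 to 1.75 on average in the settings tried. It can be larger in single small cohorts. These figures rest on assumed response timing and progression rates.

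Consequences are limited. TTR in Part A is descriptive, no hypothesis test is planned, and the ORR stands.

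**What to change.** In SAP 5.6.2.3, delete the two TTR censoring sentences and the Kaplan-Meier percentiles for TTR. Replace them with a descriptive summary (n, median, range) in confirmed responders only, the population already used for DOR, and keep the listing.

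If the time course of response in the whole group is of interest, add a cumulative incidence curve. Progression or death should be the competing event, and only patients without either should be censored. The at-least-6 limit used for the other efficacy summaries can apply to it.

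The cost is SAP wording and one simpler table. Data collection and the other efficacy analyses do not change.
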